2.2 Study Objectives

2.2.1 Primary Objective

To evaluate the long term (12-month) safety of a 2 mg/mL and 10 mg/mL intrathecal hydromorphone hydrochloride formulation given by the intrathecal route of administration.

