The purpose of this SAP is to outline the planned analyses to be completed to support the Clinical Study Report (CSR) for Protocol CNS-HYD202US. The planned analyses identified in this SAP will be included in regulatory submissions and/or future manuscripts. Also, exploratory analyses not necessarily identified in this SAP may be performed to support the clinical development program. Any post-hoc or unplanned analyses not identified in this SAP will be clearly identified in the CSR.

Additionally, the purpose of this Amended SAP is to clarify the analyses to be performed as well as the timing of various analyses. During the course of the trial, the Sponsor changed from Mallinckrodt Pharmaceuticals, Inc. (MNK) to Piramal Critical Care, LTD. (Piramal). As occurs with such changes, the priorities for the study differed from the original plans. Piramal made a business decision to proceed with only certain analyses of the study. All subjects completed the study as planned and all data pertaining to the selected safety analyses were cleaned and queried through 08 January 2018, due to the decision to analyze only safety data. Database lock occurred on 07 February 2018. Subsequently, Piramal made the decision to go forward with the entire analysis of the study. No further cleaning of the data modules was performed. This Amended SAP described the updates in the conduct and analysis of the trial due to these decisions.

3 Study Objectives

The purpose of this clinical study is to demonstrate the long term safety of a 2 mg/mL and 10 mg/mL formulation of hydromorphone hydrochloride dosed by the intrathecal route of administration in subjects with chronic pain that require continuous opioid treatment through an implantable micro-infusion pump.

Primary Objective

To evaluate the long-term (12-month) safety of 2 mg/mL and 10 mg/mL hydromorphone hydrochloride given by the intrathecal route of administration.

4 Study Design

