Data management, including database design, development of the data dictionary, and coding of adverse events and medications will be performed at Social and Scientific Services (S-3), the CRO managing data base entry and cleaning. Data will be entered into electronic case report forms (eCRFs) at the study sites. All eCRFs will be 100% source verified against corresponding source documentation (e.g., office and clinical laboratory records) for each subject. Clinical monitors will evaluate periodically the progress of the study, including the verification of appropriate consent form procedures, review of drug accountability and preparation procedures, adherence to dosing procedures, and the verification of the accuracy and completeness of eCRFs. Clinical monitors will also ensure that all protocol requirements, applicable FDA regulations, other requirements, and Investigator's obligations are being fulfilled.

Refer to the Data Management Plan for further details.

6 Definition of Populations

The **Safety Population** includes all subjects who receive any study medication (i.e. hydromorphone hydrochloride intrathecal treatment). All summaries of safety data will be carried out using the safety population. The **Intent-to-Treat (ITT) Population** also includes all subjects who receive any study medication. The analysis of the secondary endpoints will be carried out on the ITT Population. Inclusion in the Safety and ITT Populations will be determined programmatically from the eCRF data.

Exclusion of Subjects from Site 028

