8.7 Comments on Statistical Analysis

The following general comments apply to all statistical analyses and data presentations:

- Unless otherwise noted, tables will present summaries by formulation concentration (2 mg/mL and 10 mg/mL) and all subjects.
- Summaries will include frequency and percentages for categorical data and frequency, mean, standard deviation, median, minimum, and maximum for quantitative data.
- Duration variables will be calculated using the general formula: duration = (end date start date) + 1.
- Individual subject listings of all data represented on the eCRFs will be provided to facilitate the investigation of tabulated values and to allow for the clinical review of all data.
- Version 9.1 or greater of SAS statistical software package will be used to provide all summaries, listings, and graphs described in this document.
- All raw data will be presented to the original number of data places. The means and medians will be presented to one more decimal place than the raw data. The standard deviations will be presented to two more decimal places than the raw data. For averages of averages, the means and medians will also be presented to one more decimal place than the raw data and the standard deviations will also be presented to two more decimals places than the raw data.
- Generally, the denominator for percentages will be based on the number of subjects in the study population. However, for cases where appropriate, the denominator for percentages will be based on the number of subjects with non-missing data. Unless otherwise noted, all percentages will be presented to one decimal place.

9 Statistical Analyses

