9.1 Subject Disposition

The number and percent of subjects in the Safety population will be summarized. The number and percent of subjects who enrolled in the study, completed the study, withdrew from the study and their reasons for withdrawal will also be tabulated. The number and percentage of subjects who rolled over from study CNS-HYD201US, subjects who were naïve to intrathecal opioids, and those who had prior opioid treatment will also be summarized. Subject disposition will be summarized using all enrolled subjects. Enrolled subjects will be those subjects who signed the informed consent form.

A listing summarizing whether subjects completed or discontinued from the study will also be presented and the primary reason for discontinuation will be provided for those subjects who withdrew.

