9.5.1 Adverse Events

Unless otherwise noted, analyses will be based on treatment-emergent adverse events (TEAEs), defined as those events that begin or worsen in severity after the first treatment with study drug at Baseline. For AEs with missing start dates, the AE will be considered treatment-emergent unless there is additional information indicating that the AE started prior to the first study drug treatment.

Adverse events will be coded to system organ class and preferred term using MedDRA; the dictionary version will be noted in the CSR. AE severity will be assessed and summarized using

the Common Terminology Criteria for Adverse Events (CTCAE) v 4.03.

AE incidence tables will include the number and percentage of subject reporting at least one AE, as well as, the number and percentage of AEs summarized by MedDRA system organ class and preferred term. Subjects with two or more AEs in the same system organ class will be counted once for that system organ class; likewise for preferred term. For 'by severity' and 'by relationship to study treatment' tables, subjects will be counted once at the maximum severity and at the strongest causal relationship, respectively. Summaries of treatment-related AEs will include those events classified by the investigator as having a possible or probable relationship to study drug (or unknown relationship). Tables will be produced for the following: TEAEs, treatment-related TEAEs, TEAEs by strongest relationship, TEAEs by maximum severity, treatment-emergent serious adverse events (TESAEs), TESAEs by strongest relationship, treatment-related SAEs, and TESAEs by maximum severity. An overall AE summary table will provide top level subject counts for all the AE analyses noted. In addition, the AE summary table will include the number and percentage of subjects reporting any AE (including non TEAEs), the number and percentage of subjects with an AE that led to withdraw of study drug, and the number and percentage of subjects with an AE with outcome of death.

Complete listings of all AEs will be provided (non TEAEs will be flagged with a '*'). In addition, data listings of all SAEs, AEs leading to discontinuation, and AEs leading to death will also be provided.

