Appendix B

The following two Memos-to-File document the closure of Site 028.

June 3, 2015

[name]. Research Concepts Advanced Invasive Pain Management [name]

SUBJECT: CNS-HYD201US and CNS-HYD202US Study Site Non-Compliance with Good Clinical Practice ("GCP")

Dear [name]:

Between May 20 and 22, 2015, Mallinckrodt Inc. ("Mallinckrodt") conducted a "for cause" audit of your study site for CNS-HYD201US and CNS-HYD202US after receiving reports of GCP non-compliance from your study monitor. Our colleague, [name], completed an in-depth inspection of study-related records and documents and conducted interviews with you, the sub-investigator, and several study staff members. The audit revealed a lack of adequately trained and qualified study staff members, insufficient investigator oversight and poor documentation practices.

Based upon these findings, Mallinckrodt has decided to discontinue, effective immediately, conducting both CNS-HYD201US and CNS-HYD202US at your study site. For each study, we ask that you take the following steps as *soon as possible*:

- Schedule all active study participants for final study visits as described in each study protocol;
- Create an action plan that ensures the study drug is removed from the implanted pumps of study participants and replaced with non-study drug; and
- · Complete a study close-out with your Institutional Review Board ("IRB").

Your study monitor, [name], will work with you and your staff to ensure that the final study visits are completed in a timely manner and all study documents are completed appropriately. For each study, Mallinckrodt then will schedule a close-out visit to collect final study documents and facilitate return of study drug.

Your study monitor will remain your primary point-of-contact for routine, study-related questions. However, please contact [name] at [contact] or [name] at [contact] in the event you have concerns about the contents of this letter.

Sincerely

[name] Vice President, Clinical Affairs and Program Management

cc: [name] – Clinical Quality Assurance (Mallinckrodt)

[name] • [contact] T • www.mallinckrodt.com

23 November 2015

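### General AEs are summarised only as crude percentages of all dosed subjects although time at risk differs, so the figures may not equal the 12-month risk

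*SAP*

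**What the plan says.** The objective in Protocol 2.2.1 is "To evaluate the long term (12-month) safety" of the two formulations, and SAP section 3 repeats it. The primary endpoint (Protocol 3.2.1, SAP 7.1) is safety assessed by collecting AEs and SAEs during the trial, with particular attention to granuloma rates.

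For AEs in general, SAP 9.5.1 says that "AE incidence tables will include the number and percentage of subject reporting at least one AE", and adds counts and percentages of events. The Safety Population "includes all subjects who receive any study medication", and SAP 8.7 says: "Generally, the denominator for percentages will be based on the number of subjects in the study population". Neither document plans a person-time rate, a time-to-event estimate or a table by time interval for general AEs. SAP Appendix A lists a study drug exposure table, but nothing links it to AE frequency.

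Granuloma is treated differently. Protocol 14.3 plans incidence and a rate with a 95% CI. SAP 9.5.2 plans incidence and rate, without the CI. Neither defines the rate's denominator.

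On follow-up, SAP section 2 says "All subjects completed the study as planned". SAP 9.1 nevertheless provides that the numbers who "withdrew from the study and their reasons for withdrawal will also be tabulated". In SAP Appendix B the sponsor instructs the closed site: "Schedule all active study participants for final study visits as described in each study protocol".

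**The concern.** A percentage of everyone dosed estimates the risk over a stated period only if everyone is observed for that period. Here they are not:

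- Therapy runs for 12 months or until discontinuation (SAP section 4), and withdrawals are tabulated.
- Active Site 028 subjects were sent to final visits in 2015, and SAP section 6 keeps that site's data in the safety analysis.
- Titration counts for TEAEs, which start at first study-drug treatment (SAP 9.5.1), but not towards the 365 days (footnote a of the schedule of procedures). Some subjects start directly on Day 1; others have up to five titration days, 3 to 14 days apart.

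A subject who leaves at month 2 counts in the denominator as if observed to month 12. A subject with long titration contributes more than 365 days. The main safety tables would then carry percentages tied to no defined period, which are hard to read as 12-month risks or to compare with other long-term data.

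**Working it through.** **The plan's own figure.** The documents give no AE rate, dropout rate or precision target. The only relevant figure is the enrolment of about 350 to obtain 300 subjects with 6 months and 100 with 12 months of therapy. It cannot be reproduced independently: 1 − 300/350 = 14.3%, and 300/(1 − 0.143) = 350, which is circular.

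**Assumptions, for illustration only.** Dropout is independent of AEs and constant at 14.3% per 6 months. That value is borrowed from 300/350 and is not a stated retention rate. The other end of the range is no dropout. Titration, where included, is set at its extreme for every subject: 5 intervals × 14 days = 70 days, with no dropout during it.

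**Discontinuation, constant hazard.**
- Dropout hazard d = −ln(300/350)/0.5 = 0.308 per year.
- Retained at 12 months: (300/350)² = 73.5%. Mean follow-up: (1 − 0.735)/0.308 = 0.86 year.
- For true 12-month risk p, event hazard h = −ln(1 − p).
- Crude proportion = h/(h + d) × [1 − exp(−(h + d))].
- For p = 10%: h = 0.1054; 0.1054/0.4137 × (1 − 0.6612) = 0.0863, or 8.6%.

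**Discontinuation, early onset** (80% of the cumulative hazard in the first 60 days). The same formula is applied in two pieces.
- First 60 days (0.1644 year): hazard 0.8 × 0.1054/0.1644 = 0.513; contribution 0.513/0.821 × (1 − 0.8737) = 0.0789.
- Remainder (0.8356 year): hazard 0.2 × 0.1054/0.8356 = 0.0252; contribution 0.8737 × 0.0252/0.3335 × (1 − 0.7568) = 0.0161.
- Total 0.0949, or 9.5%.

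**Titration, constant hazard.**
- Risk in the extra 70 days: 1 − exp(−0.1054 × 70/365) = 0.0200.
- With dropout after Day 1: 0.0200 + 0.9800 × 0.0863 = 0.1046, or 10.5%.
- With full retention: 0.0200 + 0.9800 × 0.10 = 0.118, or 11.8%.

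| True 365-day risk | Dropout, constant hazard | Dropout, early onset | Dropout + 70 days | Full retention + 70 days | Full retention, no titration |
|---|---|---|---|---|---|
| 10% | 8.6% | 9.5% | 10.5% | 11.8% | 10% |
| 20% | 17.3% | 19.0% | 20.8% | 23.4% | 20% |
| 50% | 43.8% | 47.9% | 50.8% | 56.2% | 50% |

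**AE windows set side by side.** Any time at risk needs a start and an end, and the documents give several.
- Protocol 5.1: from study-drug administration, titration included, to the final visit.
- Protocol 13.1: from first administration on Day 1 until after study medication is discontinued.
- Protocol 13.2.1: from informed consent to a follow-up telephone call, which has no row in the schedule of procedures.
- SAP 9.5.1: TEAEs start after first study-drug treatment at Baseline.

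SAP 9.5.1 also counts an AE with a missing start date as treatment-emergent unless other information shows otherwise, and SAP 8.5 bars imputation. Such an event enters n (%) but has no event time.

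**The case against.** The best defence is that this is a single-arm descriptive study with no formal testing, so there is no between-arm exposure imbalance to correct. If discontinuation is viewed as a competing event, the crude proportion is a legitimate on-treatment risk. Disposition, AEs leading to withdrawal and the exposure table also show readers that follow-up differs. This is fair, and it is why n (%) should stay. But the SAP never says that an on-treatment risk is what it intends, and separate tables do not let a reader recover a rate or a 12-month risk.

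Several stronger readings are tempting but unsupported:

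- *The objective asks for a 12-month incidence.* It asks for an evaluation of long-term (12-month) safety, and the endpoint is AEs and SAEs collected during the trial. No 12-month risk is named.
- *Granuloma gets only crude percentages.* A rate is already planned. The gaps are its undefined denominator and the CI missing from the SAP.
- *300/350 and 100/350 are retention rates.* They are the point at which analysis may begin; SAP 8.4 expects that some subjects could still be on treatment then. That early cut does not apply to the locked data, which followed the end of participation.
- *The completion sentence is false.* SAP 8.4 elsewhere speaks of subjects who completed or discontinued early, and the sentence can be read that way. It cannot mean that everyone had 12 months.

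**Conclusion.** The point holds in a limited form. General TEAEs, treatment-related TEAEs and TESAEs have no measure that accounts for unequal time at risk, and a better one is available for a 12-month safety objective.

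A reader might infer that the percentages always make the drug look safer. The documents do not support that: discontinuation pulls the crude figure down and titration time pushes it up. Across the assumed scenarios, a true 10% shows as anything from 8.6% to 11.8%, and as exactly 10% with full retention and no titration. The numbers of withdrawals and of active subjects at Site 028, and the actual titration times, are not given, so neither size nor direction can be fixed. The illustration also rests on dropout unrelated to AEs, which may fail where AEs cause the withdrawal.

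**What to change.** 1. Reconcile the AE windows in Protocol 5.1, 13.1 and 13.2.1 with the TEAE definition in SAP 9.5.1, and state when the window ends.
2. Keep n (%). For the all-subjects column of the TEAE, treatment-related TEAE and TESAE tables, add subjects with a first event per 100 subject-years with 95% CI, and a 12-month cumulative incidence with 95% CI. Time runs from the first study-drug dose in this study, titration included, to first event or end of the AE window. State how discontinuation is handled: censoring at the end of the window gives the Kaplan-Meier form, whereas treating it as competing gives an on-treatment risk. The columns by concentration are left out because subjects may move from 2 to 10 mg/mL, and time would need its own allocation rule.
3. State how AEs with missing start dates enter the time-to-event estimate.
4. For granuloma, use the same subject-year denominator for the planned rate and carry the protocol's 95% CI into SAP 9.5.2.
5. Clarify, rather than delete, the completion sentence in SAP section 2, so that it reads as completed or discontinued early.

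Protocol 5.1 has AE onset dates recorded, and SAP Appendix A already lists dose and interruption data, so no new data should be needed. The cost is a little extra programming and possibly less favourable AE figures.

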9.5.2 Granulomas

Signs and symptoms of an inflammatory granuloma, including radicular pain, sudden loss of drug efficacy that is not attributed to other assignable causes, and spinal cord compression at the level of the catheter tip will be monitored. If there are signs or symptoms identified which may indicate an inflammatory mass formation, an MRI (with and without contrast) or CT scan will be performed to evaluate the potential presence of an inflammatory granuloma as opposed to other catheter related problems that may result in reduced delivery or clinical symptoms.

All data captured with regard to possible or confirmed inflammatory granulomas will be listed, including the date of clinical evaluation for an inflammatory mass, signs and/or symptoms of the granuloma, and all MRI or CT scan results. The incidence and rate of possible inflammatory granuloma, as well as, the incidence and rate of confirmed granuloma will be summarized by study drug concentration and all subjects.

The method of inflammatory granuloma assessment will be summarized by the number and percentage of subjects in the following categories:

- Subjects with clinical signs and symptoms of a granuloma
- Subjects with clinical signs and symptoms of granuloma, but MRI/CT not performed
- Subjects with clinical signs and symptoms of granuloma, MRI/CT performed

• Subjects with confirmed granuloma by MRI/CT via independent radiologist

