In a surveillance study Deer (49) found that the majority of cases reported in the literature were due to morphine. Among 208 subjects receiving intrathecal therapy, 3% (6/208) were found to have a significant lesion by imaging. Five were asymptomatic. No specific characteristics, such as drugs or concentrations were identified. All 6 subjects had percutaneous catheter revisions without complication. The Coffey et. al. (47) publication reviewed more than 40 cases of suspected granulomas, of which most were caused by mixtures of opioids and other agents, but some were from the use of only morphine or hydromorphone hydrochloride. Thus the risk of a granuloma exists, but given the low number of reports compared to the high utilization of intrathecal pumps to administer morphine or hydromorphone hydrochloride, the actual frequency of such events is considered extremely low

Symptoms from granulomas are motor weakness, sensory loss, changes in reflex functions, and bladder dysfunction. Other symptoms can be numbness, tingling, burning, hyperesthesia, hyperalgesia, and radicular pain at the same level as the catheter tip. A granuloma is suspected when the required amount of opioids increases for the same amount of analgesia effect and pain control (49). Precipitated drug, however, can mimic a granuloma, which are usually distinct, globular spheroid-shaped lesions best visualized on T1 MR image sequences with gadolinium contrast (46). Preliminary evidence suggests that dural mast cell degranulation and concomitant release of inflammatory mediators such as histamine may be responsible for the formation of these (48). In animal studies, however, opiates at equianalgesic doses differ in the rate of granuloma formation (50, 51).

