Granulomas have been reported most commonly with morphine. Other drugs have also been implicated in causing this complication, including hydromorphone hydrochloride, fentanyl, and tramadol (8, 51, 52). Animal studies in the sheep may indicate that at equivalent daily doses (eg, 10 mg/day) hydromorphone hydrochloride has less potential to induce an inflammatory mass or granuloma than morphine (18, 30). Given that hydromorphone hydrochloride is at least five-times more potent than morphine, these observations may explain the belief of physicians that hydromorphone hydrochloride has fewer side effects and potential for granuloma in that the dose and concentration at the catheter tip during infusion is far less with hydromorphone hydrochloride than morphine. Given the daily dose and concentration are considered the primary factors that induce a granuloma the lower dose and slower infusion rate resulting in a lower

concentration in the area of the catheter tip, would be predicted based on these animal models to have a lower potential of granuloma formation than with intrathecal morphine.

In addition to the literature, Medtronic Inc. has conducted a large publicly available post-approval surveillance study for the SynchroMed[®] II Programmable Pump that also includes surveillance of various drug products delivered by IT administration. This study followed 4,384 subjects with implanted SynchroMed[®] II Programmable Pump drug delivery systems at fifty centers, with 3,101 subjects receiving various other IT medications for pain. This study also included subjects receiving intrathecal morphine (Infumorph). Medtronic's study was a careful examination of granuloma formation in subjects. A granuloma in the Medtronic surveillance study was defined as "an intradural extra medullary mass at the catheter tip that could be visualized by enhanced MRI imaging." The criteria for diagnosing such a granulomatous mass is based on several clinical signs and symptoms: a decrease of drug effect and new radicular pain and/or cord compression, MRI findings of an enhancing mass at the catheter tip on the T-1 infusion and surgical or histological confirmation.

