3.0 STUDY DESIGN

3.1 Description of Trial Design

This is an open-label, single-arm study to evaluate the safety of hydromorphone hydrochloride given by continuous intrathecal infusion using an implantable pump device. This clinical trial will be conducted at up to 30 clinical trial sites that are experienced with the use of intrathecal opioids. This study will enroll both subjects on a current opioid (eg, morphine or hydromorphone hydrochloride) intrathecal medication as well as naïve subjects not currently on intrathecal opioid medications. Dosing regimens allowed in this study will include simple continuous, complex continuous and Personal Therapy Manager (PTM) dosing.

For subjects entering the trial already on a therapeutic dose of another intrathecal hydromorphone hydrochloride, the hydromorphone hydrochloride will be replaced by the study

drug (hydromorphone hydrochloride for intrathecal injection) on a 1:1 basis without dose adjustment or optional titration days. The subject is considered at a therapeutic dose and will start the study on Day 1.

Subjects converted from an intrathecal opioid therapy other than hydromorphone hydrochloride to the study drug will be dosed with the study drug according to the following conversion scheme:

Subject on Morphine or on another Opioid ³	Conversion Ratio
Dose ≤ 30 mg IT morphine and tolerating therapy well	1:61
Dose > 30 mg IT morphine or subject has significant side effects on morphine	1:12 ²

¹Conversion is based on mg-morphine equivalence such that for each 6 mg morphine sulfate the dose is converted to 1 mg hydromorphone hydrochloride.

Subjects who are converted directly to the study drug based on the 1:6 morphine-equivalence ratio are, by definition, at a therapeutic dose and must start the study on Day 1 without titration. Dose adjustments may be performed at subsequent visits, based on the investigator discretion.

For subjects using 1:12 conversion ratio, due to safety considerations, the conversion will be followed by up to five (5) optional titration days (Titration Days A, B, C, D and E) to achieve a therapeutic dose that is well tolerated before starting Day 1. These optional titration days may be three (3) to fourteen (14) days apart.

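### SAP 9.5.2 counts granulomas and granuloma signs without requiring onset or worsening after first study drug, and plans the table on all consented subjects

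*SAP*

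**What the plan says.** **Counting rule.** SAP 9.5.2 states "All data captured with regard to possible or confirmed inflammatory granulomas will be listed". It then plans the incidence and rate of possible granuloma and that "the incidence and rate of confirmed granuloma will be summarized by study drug concentration and all subjects". A further summary of assessment method begins with the row "Subjects with clinical signs and symptoms of a granuloma". None of these refers to first study drug.

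**Rule for adverse events.** SAP 9.5.1 bases its analyses on treatment-emergent events, "defined as those events that begin or worsen in severity after the first treatment with study drug at Baseline". SAP 9.5.2 neither repeats nor cites this.

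**Population.** SAP 9.5 assigns safety to the Safety population (dosed subjects). SAP Appendix A plans Table 14.3.5.4, the granuloma table, on All Enrolled Subjects, and SAP 9.1 says "Enrolled subjects will be those subjects who signed the informed consent form".

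**Timing of evaluations.** Protocol Appendix A and SAP Table 1 both place the clinical granuloma evaluation at Screening. For subjects from CNS-HYD201US it is taken from that trial's final visit. It then runs from Day 1 to Day 365.

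**Who enters.** Protocol 3.1 admits "both subjects on a current opioid (eg, morphine or hydromorphone hydrochloride) intrathecal medication" as well as naïve subjects, and gives a conversion scheme from morphine. The share in each group is not stated.

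**Background.** Protocol 1.3.3 notes "Granulomas have been reported most commonly with morphine". It cites a surveillance series of 208 intrathecal patients in which "3% (6/208) were found to have a significant lesion by imaging", five of the six being asymptomatic, and a device surveillance study with 12 cases among 4,384 subjects.

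**The concern.** Granuloma is the event singled out in the primary endpoint (Protocol 3.2.1, SAP 7.1), and the protocol's background associates it mainly with morphine. Some subjects move from intrathecal morphine to study drug through a pump they already have. If signs recorded before the first fill, or a mass that predates it, go into the summary, the table reports a finding from previous therapy in a 2 mg/mL or 10 mg/mL hydromorphone column.

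The signs-and-symptoms row is the most exposed. SAP 9.5.2 lists radicular pain among the signs, and Protocol 3.3 also lists a change in the character, quality or intensity of pain. Both are non-specific in a population selected for intractable pain. With about one event expected, a single wrongly attributed case is large relative to the count.

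**Working it through.** **1. Do the passages allow a pre-drug finding to be counted?**

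- Pre-drug granuloma data exist by design (Screening and roll-over Baseline).
- The 9.5.2 summaries carry no date limit, while 9.5.1 does.
- The planned table population does not require dosing.
- No eligibility criterion names an existing or suspected catheter-tip mass. Exclusion 5 covers a known central nervous system contraindication, and exclusion 9 leaves fitness to the investigator.
- Imaging is done only on suspicion (Protocol 3.3), so an asymptomatic mass passes Screening.
- Protocol 3.1 and SAP section 4 say granuloma events will be classified by duration and concentration of hydromorphone. SAP 9.5.2 carries through concentration but not duration.

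Followed as written, the table can include signs or lesions that precede study drug.

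**2. Reproduce the protocol's figures.** 12/4384 = 0.274% (stated 0.27%). 6/208 = 2.88% (stated 3%).

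**3. Expected count.** 350 × 12/4384 = 0.96 events. This assumes that the surveillance proportion carries over to this trial.

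**4. Effect of one case.** Protocol 14.3 plans a 95% CI but names no method. I assume exact (Clopper-Pearson) limits and a simple proportion.

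| Cases / N | Estimate | 95% CI |
|---|---|---|
| 0/350 | 0% | 0 to 1.05% |
| 1/350 | 0.29% | 0.01 to 1.58% |
| 2/350 | 0.57% | 0.07 to 2.05% |

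A concentration column is smaller. If one held 100 subjects (an assumption; the split is not given), one case would move it from 0% (0 to 3.6%) to 1.0% (0.03 to 5.4%).

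**5. How many lesions might be present at entry?** Assume 10% to 75% of 350 subjects, that is 35 to 262.5, have prior intrathecal therapy.

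| Prevalence applied | Expected lesions |
|---|---|
| 5/208, silent | 0.8 to 6.3 |
| 1/208, symptomatic | 35/208 = 0.2 to 262.5/208 = 1.3 |
| 12/4384, all | 0.1 to 0.7 |

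An onset rule can act on lesions or signs recognised before the first fill, roughly the second row. The silent lesions in the first row are not counted unless they become symptomatic. If they do so after the first fill, an onset rule counts them too.

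**The case against.** **Other text may already cover this.** The endpoint is assessed through adverse events, and SAP 9.5.1 makes treatment-emergent the default unless otherwise noted. Protocol 5.2.1 and SAP 9.2.2 treat existing conditions as baseline and count only adverse changes. This has force: a granuloma known at Screening should drop out of the adverse-event tables. But the default sits in the adverse-event subsection, while 9.5.2 draws on separate evaluation and imaging data (Listings 16.2.11.1 to 16.2.11.4) and its table uses another population. The text leaves two readings open for the endpoint's named event.

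**The Screening-positive path is narrow.** Signs prompt imaging and notice to the Medical Monitor, exclusions 5 and 9 can apply, and Protocol 15.1 completes case report forms only for dosed subjects, so the two populations may nearly coincide in practice. This stands as a limit on frequency. It does not close the path, because Screening and first dosing may be one visit (Protocol 9.1), and none of these is an analysis rule.

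**Counting every case is conservative.** For a rare serious harm that is a fair preference. It is met by keeping the all-cases total visible beside the restricted rate.

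**Stronger readings a reader might infer.** One is that many subjects arrive on morphine and that several carried-over lesions will inflate the rate. The documents give no share, and most lesions in the cited imaging series were silent. Another is that one or two cases decide the result. The protocol synopsis rules out formal testing and no threshold or morphine comparison is planned; the intervals in the working overlap heavily. A third is that a negative Screening evaluation should be required. That could discard a true new or worsening granuloma in a subject with non-specific pain at entry, or a roll-over lesion that arose on hydromorphone.

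**Conclusion.** The gap is real and limited. The granuloma summary lacks the onset rule that the SAP applies to adverse events, and its planned population conflicts with SAP 9.5, so findings that precede study drug can be reported under a hydromorphone concentration. With about one event expected in 350, one such case would account for the whole expected count, although the absolute shift is 0.29 percentage points. How often this would happen cannot be determined from the documents: it depends on the unstated share with prior intrathecal therapy and on whether investigators dosed subjects who had signs at Screening. An onset rule improves attribution but does not settle it, since silent pre-existing lesions stay indistinguishable without baseline imaging. The change should be made because it is cheap and concerns the event named in the primary endpoint.

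**What to change.** 1. **Rule and population.** In SAP 9.5.2 and Table 14.3.5.4, use the Safety population. Define the study-drug granuloma rate as events whose signs or lesion begin or worsen after the first study drug fill in this trial or, for CNS-HYD201US roll-overs, after first hydromorphone study drug in that trial. Do not require a negative Screening evaluation: a subject with non-specific signs at entry who later has a new or worsening granuloma still counts.
2. **Keep everything visible.** Show the all-cases total beside this rate. Put subjects with signs or a lesion before first study drug in a separate row, by entry route.
3. **Attribution display.** For each case, tabulate days from first study drug to first sign. Give the rate by prior intrathecal therapy: never exposed; prior or current morphine or other opioid; prior hydromorphone; CNS-HYD201US roll-over. Classify subjects weaned off intrathecal therapy as previously exposed. Protocol 3.1 describes naïve subjects as not currently on intrathecal opioids, and Protocol 9.3 handles weaned subjects together with naïve ones, so the naïve label alone does not establish absence of exposure.

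**Cost.** SAP wording and one table, with no new assessments. Evaluation dates, signs, imaging, pump and dose-conversion data are already listed. Two derivations need care: roll-overs need their first hydromorphone date from CNS-HYD201US, and previous exposure has to come from the pump and treatment history, because prior medications reach back only 30 days. The database was locked on 07 February 2018, so the restricted rate should be labelled as a clarification made after lock. Subgroup counts will be small, and silent pre-existing lesions in switched subjects still cannot be excluded.
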